11.2 Definitions of Measurable and Non-Measurable Disease

11.21 Measurable Disease

- 11.211 A non-nodal lesion is considered measurable if its longest diameter can be accurately measured as ≥ 2.0 cm with chest x-ray, or as ≥ 1.0 cm with CT scan, CT component of a PET/CT, or MRI.
- 11.212 A superficial non-nodal lesion is measurable if its longest diameter is ≥ 1.0 cm in diameter as assessed using calipers (e.g. skin nodules) or imaging. In the case of skin lesions, documentation by color photography, including a ruler to estimate the size of the lesion, is recommended.
- 11.213 A malignant lymph node is considered measurable if its short axis is >1.5 cm when assessed by CT scan (CT scan slice thickness recommended to be no greater than 5 mm).

Tumor lesions in a previously irradiated area are considered measurable disease under the following conditions:

- a) New lesion that has developed after radiation is completed
- b) Definite increase in the size of the previously irradiated lesion.

11.22 Non-Measurable Disease

- 11.221 All other lesions (or sites of disease) are considered non-measurable disease, including pathological nodes (those with a short axis ≥ 1.0 to <1.5 cm). Bone lesions, leptomeningeal disease, ascites, pleural/ pericardial effusions, lymphangitis cutis/pulmonis, inflammatory breast disease, and abdominal masses (not followed by CT or MRI), are considered as non-measurable as well.

Note: 'Cystic lesions' thought to represent cystic metastases can be considered as measurable lesions, if they meet the definition of measurability described above. However, if non-cystic lesions are present in the same patient, these are preferred for selection as target lesions. In addition, lymph nodes that have a short axis <1.0 cm are considered non-pathological (i.e., normal) and should not be recorded or followed.

11.3 Guidelines for Evaluation of Measurable Disease

11.31 Measurement Methods:

- All measurements should be recorded in metric notation (i.e., decimal fractions of centimeters) using a ruler or calipers.
- The same method of assessment and the same technique must be used to characterize each identified and reported lesion at baseline and during follow-up. For patients having only lesions measuring at least 1 cm to less than 2 cm must use CT imaging for both pre- and post-treatment tumor assessments.
- Imaging-based evaluation is preferred to evaluation by clinical examination when both methods have been used at the same evaluation to assess the antitumor effect of a treatment.

11.32 Acceptable Modalities for Measurable Disease:

Conventional CT and MRI: This guideline has defined measurability of lesions on CT scan based on the assumption that CT slice thickness is 5 mm or less. If CT scans have slice thickness greater than 5 mm, the minimum size for a measurable lesion should be twice the slice thickness.

- As with CT, if an MRI is performed, the technical specifications of the scanning sequences used should be optimized for the evaluation of the type and site of disease. The lesions should be measured on the same pulse sequence. Ideally, the same type of scanner should be used and the image acquisition protocol should be followed as closely as possible to prior scans. Body scans should be performed with breath-hold scanning techniques, if possible.
- PET-CT: If the site can document that the CT performed as part of a PET-CT is of identical diagnostic quality to a diagnostic CT (with IV and oral contrast), then the CT portion of the PET-CT can be used for RECIST measurements and can be used interchangeably with conventional CT in accurately measuring cancer lesions over time.
- Chest X-ray: Lesions on chest x-ray are acceptable as measurable lesions when they are clearly defined and surrounded by aerated lung. However, CT scans are preferable.
- Physical Examination: For superficial non-nodal lesions, physical examination is acceptable, but imaging is preferable, if both can be done. In the case of skin lesions, documentation by color photography, including a ruler to estimate the size of the lesion, is recommended.
- FDG-PET: FDG-PET scanning is allowed to complement CT scanning in assessment of progressive disease [PD] and particularly possible 'new' disease. A 'positive' FDG-PET scanned lesion is defined as one which is FDG avid with an update greater than twice that of the surrounding tissue on the attenuation corrected image; otherwise, an FDG-PET scanned lesion is considered 'negative.' New lesions on the basis of FDG-PET imaging can be identified according to the following algorithm:
 - a. Negative FDG-PET at baseline with a positive FDG-PET at follow-up is a sign of PD based on a new lesion.
 - b. No FDG-PET at baseline and a positive FDG-PET at follow-up:

- i. If the positive FDG-PET at follow-up corresponds to a new site of disease confirmed by CT, this is PD.
- ii. If the positive FDG-PET at follow-up is not confirmed as a new site of disease on CT at the same evaluation, additional follow-up CT scans (i.e., additional follow-up scans at least 4 weeks later) are needed to determine if there is truly progression occurring at that site. In this situation, the date of PD will be the date of the initial abnormal PDG-PET scan.
- iii. If the positive FDG-PET at follow-up corresponds to a pre-existing site of disease on CT that is not progressing on the basis of the anatomic images, it is not classified as PD.

11.33 Measurement at Follow-up Evaluation:

A subsequent scan must be obtained 8 weeks following initial documentation of an objective status of either complete response (CR) or partial response (PR).

In the case of stable disease (SD), follow-up measurements must have met the SD criteria at least once after study entry at a minimum interval of 8 weeks (see Section 11.44).

The cytological confirmation of the neoplastic origin of any effusion that appears or worsens during treatment when the measurable tumor has met criteria for response or stable disease is mandatory to differentiate between response or stable disease (an effusion may be a side effect of the treatment) and progressive disease.

- Cytologic and histologic techniques can be used to differentiate between PR and CR in rare cases (e.g., residual lesions in tumor types such as germ cell tumors, where known residual benign tumors can remain.)

11.4 Measurement of Effect

11.41 Target Lesions & Target Lymph Nodes

- Measurable lesions (as defined in Section 11.21) up to a maximum of 5 lesions representative of all involved organs, should be identified as “Target Lesions” and recorded and measured at baseline. These lesions can be non-nodal or nodal (as defined in 11.21), where no more than 2 lesions are from the same organ and no more than 2 malignant nodal lesions are selected.
Note: If fewer than 5 target lesions and target lymph nodes are identified (as there often will be), there is no reason to perform additional studies beyond those specified in the protocol to discover new lesions.
- Target lesions and target lymph nodes should be selected on the basis of their size, be representative of all involved sites of disease, but in addition should be those that lend themselves to reproducible repeated measurements. It may be the case that, on occasion, the largest lesion (or malignant lymph node) does not lend itself to reproducible measurements in which circumstance the next largest lesion (or malignant lymph node) which can be measured reproducibly should be selected.
- Baseline Sum of Dimensions (BSD): A sum of the longest diameter for all target lesions plus the sum of the short axis of all the target lymph nodes will be calculated and reported as the baseline sum of dimensions (BSD). The

BSD will be used as reference to further characterize any objective tumor response in the measurable dimension of the disease.

- Post-Baseline Sum of the Dimensions (PBSD): A sum of the longest diameter for all target lesions plus the sum of the short axis of all the target lymph nodes will be calculated and reported as the post-baseline sum of dimensions (PBSD). If the radiologist is able to provide an actual measure for the target lesion (or target lymph node), that should be recorded, even if it is below 0.5 cm. If the target lesion (or target lymph node) is believed to be present and is faintly seen but too small to measure, a default value of 0.5 cm should be assigned. If it is the opinion of the radiologist that the target lesion or target lymph node has likely disappeared, the measurement should be recorded as 0 cm.
- The minimum sum of the dimensions (MSD) is the minimum of the BSD and the PBSD.

11.42 Non-Target Lesions & Non-Target Lymph Nodes

Non-measurable sites of disease (Section 11.22) are classified as non-target lesions or non-target lymph nodes and should also be recorded at baseline. These lesions and lymph nodes should be followed in accord with 11.433.

11.43 Response Criteria

11.431 All target lesions and target lymph nodes followed by CT/MRI/PET-CT/Chest X-ray/physical examination must be measured on re-evaluation at evaluation times specified in Section 11.1. Specifically, a change in objective status to either a PR or CR cannot be done without re-measuring target lesions and target lymph nodes.

Note: Non-target lesions and non-target lymph nodes should be evaluated at each assessment, especially in the case of first response or confirmation of response. In selected circumstances, certain non-target organs may be evaluated less frequently. For example, bone scans may need to be repeated only when complete response is identified in target disease or when progression in bone is suspected.

11.432 Evaluation of Target Lesions

Complete Response (CR): All of the following must be true:

- Disappearance of all target lesions.
- Each target lymph node must have reduction in short axis to <1.0 cm.

Partial Response (PR): At least a 30% decrease in PBSD (sum of the longest diameter for all target lesions plus the sum of the short axis of all the target lymph nodes at current evaluation) taking as reference the BSD (see Section 11.41).

Progression (PD): At least one of the following must be true:

- At least one new malignant lesion, which also includes any lymph node that was normal at baseline (<1.0 cm short axis) and increased to ≥ 1.0 cm short axis during follow-up.
- At least a 20% increase in PBSD (sum of the longest diameter for all target lesions plus the sum of the short axis of all the target lymph nodes at current evaluation) taking as reference the

MSD (Section 11.41). In addition, the PBSD must also demonstrate an absolute increase of at least 0.5 cm from the MSD.

- c. See Section 11.32 for details in regards to the requirements for PD via FDG-PET imaging.

Stable Disease (SD): Neither sufficient shrinkage to qualify for PR, nor sufficient increase to qualify for PD taking as reference the MSD.

11.433 Evaluation of Non-Target Lesions & Non-target Lymph Nodes

Complete Response (CR): All of the following must be true:

- a. Disappearance of all non-target lesions.
- b. Each non-target lymph node must have a reduction in short axis to <1.0 cm.

Non-CR/Non-PD: Persistence of one or more non-target lesions or non-target lymph nodes.

Progression (PD): At least one of the following must be true:

- a. At least one new malignant lesion, which also includes any lymph node that was normal at baseline (<1.0 cm short axis) and increased to ≥1.0 cm short axis during follow-up.
- b. Unequivocal progression of existing non-target lesions and non-target lymph nodes. (NOTE: Unequivocal progression should not normally trump target lesion and target lymph node status. It must be representative of overall disease status change.)
- c. See Section 11.32 for details in regards to the requirements for PD via FDG-PET imaging.

11.44 Overall Objective Status

The overall objective status for an evaluation is determined by combining the patient's status on target lesions, target lymph nodes, non-target lesions, non-target lymph nodes, and new disease as defined in the following tables:

11.441 For Patients with Measurable Disease

Target Lesions & Target Lymph Nodes	Non-Target Lesions & Non-Target Lymph Nodes	New Sites of Disease	Overall Objective Status
CR	CR	No	CR
CR	Non-CR/Non-PD	No	PR
PR	CR Non-CR/Non-PD	No	PR
CR/PR	Not All Evaluated*	No	PR**

Target Lesions & Target Lymph Nodes	Non-Target Lesions & Non-Target Lymph Nodes	New Sites of Disease	Overall Objective Status
SD	CR Non-CR/Non-PD Not All Evaluated*	No	SD
Not all Evaluated	CR Non-CR/Non-PD Not All Evaluated*	No	Not Evaluated (NE)
PD	Unequivocal PD CR Non-CR/Non-PD Not All Evaluated*	Yes or No	PD
CR/PR/SD/PD/Not all Evaluated	Unequivocal PD	Yes or No	PD
CR/PR/SD/PD/Not all Evaluated	CR Non-CR/Non-PD Not All Evaluated*	Yes	PD

*See Section 11.431

** NOTE: This study uses the protocol RECIST v1.1 template dated 2/16/2011. For data collection and analysis purposes the objective status changed from SD to PR in the MCCC protocol RECIST v1.1 template as of 2/16/2011 and to match RECIST v1.1 requirements.

11.45 Symptomatic Deterioration

Patients with global deterioration of health status requiring discontinuation of treatment without objective evidence of disease progression at that time, and not either related to study treatment or other medical conditions, should be reported as PD due to "symptomatic deterioration." Every effort should be made to document the objective progression even after discontinuation of treatment due to symptomatic deterioration. A patient is classified as having PD due to "symptomatic deterioration" if any of the following occur that are not either related to study treatment or other medical conditions:

- Weight loss >10% of body weight.
- Worsening of tumor-related symptoms.
- Decline in performance status of >1 level on ECOG scale.

12.0 Descriptive Factors

- 12.1 Prior treatment: 1 vs 2 vs 3+
- 12.4 Primary site of tumor: Gallbladder vs intrahepatic vs extrahepatic biliary tract cancer
- 12.5 Degree of differentiation: Well vs moderately vs poorly differentiated vs undifferentiated/anaplastic vs cannot be assessed/unknown
- 12.6 ECOG performance status: 0 vs 1
- 12.7 Prior treatment with fluoropyrimidine based regimen: Yes vs no

13.0 Treatment/Follow-up Decision at Evaluation of Patient

- 13.1 Continuation of treatment

Patients who are CR, PR, or SD will continue treatment per protocol.

13.2 Progressive disease (PD)

Patients who develop PD while receiving therapy will go to the event-monitoring phase.

13.3 Off protocol treatment

Patients who go off protocol treatment for reasons other than PD will go to the event-monitoring phase per Section 4.0. Treatment decision during event-monitoring phase is at the discretion of the treating physician.

13.4 Duration of therapy for CR, PR or SD

Patients who achieve a CR, PR or SD will continue to receive treatment per protocol until they develop PD or unacceptable toxicity.

13.5 Definition of Ineligible

A patient is deemed *ineligible* if after registration, it is determined that at the time of registration, the patient did not satisfy each and every eligibility criteria for study entry. The patient may continue treatment off-protocol at the discretion of the physician as long as there are no safety concerns, and the patient was properly registered. The patient will go directly to the event-monitoring phase of the study (or off study, if applicable).

- If the patient received treatment, all data up until the point of confirmation of ineligibility must be submitted. Event monitoring will be required per Section 18.0 of the protocol.
- If the patient never received treatment, on-study material must be submitted. Event monitoring will be required per Section 4.0 of the protocol.

13.6 Definition of Major Violation

A patient is deemed a *major violation*, if protocol requirements regarding treatment in cycle 1 of the initial therapy are severely violated that evaluability for primary end point is questionable. All data up until the point of confirmation of a major violation must be submitted. The patient will go directly to the event-monitoring phase of the study. The patient may continue treatment off-protocol at the discretion of the physician as long as there are no safety concerns, and the patient was properly registered. Event monitoring will be required per Section 4.0 of the protocol.

13.7 Definition of Cancel

A patient is deemed a *cancel* if he/she is removed from the study for any reason before any study treatment is given. On-study material and the End of Active Treatment/Cancel Notification Form must be submitted. No further data submission is necessary.

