6.6 Treatment start

Treatment cannot begin prior to registration and must begin ≤ 28 days after registration.

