16.0 Statistical Considerations and Methodology

16.1 Overview

This protocol will assess the efficacy of FTD/TPI (TAS-102) in patients with refractory cholangiocarcinoma using a single stage phase II study design. This single arm Phase II trial will assess the 16-week progression-free survival rate (by RECIST v1.1) associated with FTD/TPI (TAS-102) in patients with refractory cholangiocarcinoma. We will adopt a PFS rate of 10% as the null hypothesis and PFS rate of 30% as the alternative hypothesis. In addition to response, this study will also evaluate the overall response rate (ORR), progression-free survival (PFS), overall survival (OS), and adverse events.

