16.21 Decision Rule

The largest success proportion where the proposed treatment regimen would be considered ineffective in this population is 10%, and the smallest success proportion that would warrant subsequent studies with the proposed regimen in this patient population is 30%. The following single stage design uses 25 patients to test the null hypothesis that the true success proportion in a given patient population is at most 10%. If 5 or fewer successes are observed in the 25 evaluable patients, we will consider this regimen ineffective in this patient population. If 6 or more successes are observed in the 25 evaluable patients, we may recommend further testing of this regimen in subsequent studies in this population.

NOTE: We consider a success to be alive and progression-free by 16 weeks post-registration (i.e. stable disease, partial response, or complete response).

16.22 Sample Size:

The single stage study design to be utilized is fully described in Section 16.21. A maximum of 25 evaluable patients will be accrued onto this phase II study unless undue toxicity is encountered. We anticipate accruing an additional 3 patients to account for ineligibility, cancellation, major treatment violation, or other reasons. Maximum projected accrual is therefore 28 patients.

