16.31 Primary Endpoint

16.311 **Definition:** The primary endpoint of this trial is the progression-free survival rate. This is defined as the proportion of evaluable patients who are progression-free (stable disease, partial response, complete response) at 16 weeks. All patients meeting the eligibility criteria who have signed a consent form and have begun treatment will be considered evaluable.

16.312 **Estimation:** The proportion of successes will be estimated by the number of successes divided by the total number of evaluable patients. Confidence intervals for the true success proportion will be calculated according to the approach of Clopper and Pearson.

16.316 **Over Accrual:** If more than the target number of patients are accrued, the additional patients will not be used to evaluate the stopping rule or used in any decision making processes; however, they will be included in final point estimates and confidence intervals as though they were accrued in the final stage.

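### Success is timed from registration but only treated patients are evaluable, so a recognised failure before first dose leaves the denominator; within the 28-patient cap this raises the attained error from 0.033 to at most about 0.055

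*Combined protocol and SAP*

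**What the plan says.** - **Clock.** The note in section 16.21 defines a success as "alive and progression-free by 16 weeks post-registration". Section 16.311 says only that the assessment is at 16 weeks and names no origin, so 16.21 governs. Sections 16.322 and 16.323 time PFS and OS from study entry.
- **Denominator.** Section 16.311: "All patients meeting the eligibility criteria who have signed a consent form and have begun treatment will be considered evaluable". The estimate is successes divided by evaluable patients (16.312).
- **Interval.** Section 6.6 says that treatment "must begin ≤ 28 days after registration".
- **Exit before dosing.** Section 13.7 defines a cancel as a patient "removed from the study for any reason before any study treatment is given". It asks for on-study material and a cancel notification form, and no data after that.
- **Replacement.** Section 16.22 plans 25 evaluable patients plus 3 more to cover ineligibility, cancellation, major violation or other reasons, with a projected maximum of 28.
- **A neighbouring rule.** For a patient found ineligible, section 13.5 says: "If the patient never received treatment, on-study material must be submitted. Event monitoring will be required per Section 4.0 of the protocol".

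No section counts progression or death between registration and first dose as a non-success, and no sensitivity analysis on all registered patients is planned.

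**The concern.** A treated-patient analysis set is a usual choice in a single-arm phase II trial. A registration clock is also usual. The difficulty is combining them. The days from registration to first dose count toward the 16 weeks, but a failure in those days that leads to removal is not counted. If the patients who never start have already failed, then P(success | treated) = P(success) / P(treated), which is larger than P(success) among those registered.

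The interval can be 28 of 112 days, a quarter of the endpoint window. There is no control arm, and the decision turns on one patient (5 or 6 successes in 25). A small upward shift can therefore matter, and later outcomes of cancelled patients cannot be recovered if nobody was asked to collect them.

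**Working it through.** **Inputs.** Section 16.1: "We will adopt a PFS rate of 10% as the null hypothesis" and "PFS rate of 30% as the alternative hypothesis". Section 16.21: "If 6 or more successes are observed in the 25 evaluable patients", further testing may be recommended. Section 16.22: 25 evaluable, 28 at most. Section 16.24: level 0.05.

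**Step 1: reproduce the plan's table.** P(X ≥ 6) for X ~ Bin(25, p):

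| True rate | Section 16.24 | Exact binomial |
|---|---|---|
| 0.10 | 0.033 | 0.0334 |
| 0.15 | 0.160 | 0.1615 |
| 0.20 | 0.383 | 0.3833 |
| 0.25 | 0.622 | 0.6217 |
| 0.30 | 0.807 | 0.8065 |

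The table reproduces; the largest difference is 0.0015, at 0.15.

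**Step 2: outcome-related cancels within the planned allowance.** Suppose c cancels are all pre-dose failures and are replaced, so that 25 + c register and 25 are treated. A rate p among registered patients becomes p × (25 + c)/25 among treated patients.

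| c | Rate if p = 10% | P(≥6 of 25) | Rate if p = 30% | P(≥6 of 25) |
|---|---|---|---|---|
| 0 | 10.0% | 0.033 | 30.0% | 0.807 |
| 1 | 10.4% | 0.039 | 31.2% | 0.840 |
| 2 | 10.8% | 0.046 | 32.4% | 0.868 |
| 3 | 11.2% | 0.054 | 33.6% | 0.893 |

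If only half of three cancels are failures and the rest are unrelated to outcome, the null rate becomes 0.10 × 28/26.5 = 10.6% and the probability 0.042. If no cancel is related to outcome, it stays at 0.033.

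**Step 3: ceiling.** Successes among evaluable patients cannot outnumber successes among registered patients, and at most 28 register. At a registered rate of 10%, P(6 or more) therefore cannot exceed P(Bin(28, 0.10) ≥ 6) = 0.055, whatever the delay.

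**Step 4: effect on the reported estimate.** At the cut-off, 6/25 = 24.0% (Clopper-Pearson 95% interval 9.4% to 45.1%). Counting three cancels as failures gives 6/28 = 21.4% (8.3% to 40.9%).

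**Step 5: operating characteristics after a fix.**
- 25 eligible registered patients, with pre-dose failures counted, and a cut-off of 6: error 0.033, power 0.807.
- All 28 in the decision, cut-off 6: error 0.055, power 0.887.
- All 28 in the decision, cut-off 7: error 0.018, power 0.780.

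**The case against.** Several points on the other side stand.

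- **Silent progression is not lost.** The test schedule (4.1) places no scan between registration and first dose. A patient who progresses unnoticed starts treatment and stays evaluable. The baseline scan precedes registration, so that growth counts at the first restaging. Only death, clinical deterioration or progression that happens to be detected can remove a patient. A reader might infer that the whole interval is immune from failure; the schedule does not support that.
- **Much larger figures do not fit the plan.** A reader might assume a constant hazard with 10% progression-free at day 112. The rate among the treated is then 0.10/(1 − f(1 − S)), where S = 0.1^(gap/112) and f is the share of pre-dose failures that are cancelled. A 14-day gap with f = 0.5 gives an error of 0.058, 28 days with f = 0.5 gives 0.091, and 28 days with f = 1 gives 0.28. Reaching 25 treated patients would then take about 29, 32 and 44 registrations (25 divided by the same denominator). All exceed 28, so these values are not attainable under section 16.22.
- **The bias can be bounded.** The cancel form makes the number of cancels known, and counting them all as failures gives a worst case. It would be wrong to say that nothing can be checked. What the protocol does not require is later progression or vital status. Whether the form records a reason and date is not stated.
- **PFS and OS.** Sections 16.322 and 16.323 do not restrict those analyses to treated patients, so bias there is an inference, conditional on that set being used.
- **Whose 10%?** Section 16.21 tests the null in evaluable patients, and the documents give no source for 10%. If the benchmark already describes treated patients timed from registration, the stated error holds. Nothing shows that it does.
- **Sections 13.5 and 13.7** define different categories, and 13.5 allows for going off study where applicable. They overlap only for a patient who is both ineligible and removed untreated.

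**Conclusion.** The mismatch is in the text, and its direction is upward whenever cancels are enriched for patients who have already failed. Its size is limited. If one to three of the spare places replace pre-dose failures, the null rate rises by 0.4 to 1.2 percentage points and the attained error from 0.033 to between 0.039 and 0.054, with a ceiling of 0.055. The stated 0.05 can be exceeded, but only slightly, and only if nearly all spare places are used in this way. They are also reserved for ineligibility, major violations and other reasons.

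These figures assume that the 10% null refers to registered patients and that the 28-patient cap is respected. The documents give no cancel rate or usual delay, so the effect is a range that includes none. They do not support a claim of gross error inflation, or a firm claim that PFS and OS are biased. The change is still worth making: the bias has one direction, the decision rests on a single patient, and the correction is mostly wording.

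**What to change.** Use one time origin with one analysis set.

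1. **Simplest: time from first dose.** In 16.21 and 16.311, start the 16 weeks at first dose. Do the same for PFS and OS if they are analysed in treated patients. The 6-of-25 rule and its table stay as they are, and four 28-day cycles then equal the 112-day window. The cost is that results are conditional on starting treatment, which the report should say.
2. **Alternative: keep the registration clock.** Count an eligible registered patient cancelled for progression, deterioration or death as a non-success, and base the decision on the first 25 eligible patients (error 0.033, power 0.807). The observed rate may be slightly lower. If all 28 enter the decision, the cut-off has to be re-derived, because 6 of 28 gives error 0.055 and 7 of 28 gives error 0.018 with power 0.78.

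Under either option:
- In 13.7, record the reason and date of every cancel and follow progression and vital status as in section 4.2.
- Report a sensitivity analysis that counts cancels as failures.
- State which of 13.5 and 13.7 applies to a patient who is both ineligible and untreated.

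The cost is protocol wording and brief follow-up of a few patients at most. It needs no extra patients or procedures.
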